10.6.2 Laboratory Test Results

For hematology, chemistry, and other laboratory values, the baseline values and, changes from baseline by visit, the minimum, maximum, and last observed values will be summarized descriptively.

For the summary of changes from baseline by visit, subjects without a baseline and/or post baseline value will be excluded; values from unscheduled assessments will be excluded. Subjects with missing data for a scheduled assessment time point will be excluded from the summary for that time point. Laboratory results from samples taken > 30 days after the last administration of protocol therapy will be excluded from the laboratory summaries.

Laboratory test results will be graded using the NCI CTCAE (Version 4.03). Shifts in laboratory toxicity grades to outside the normal range will be evaluated for selected laboratory parameters defined in Appendix C by assessing the maximum increase and/or decrease observed during the course of study treatment relative to the baseline toxicity grade.

The subject incidence of Grade 3 and 4 hematological laboratory abnormalities (including neutropenia, thrombocytopenia, and anemia) will be provided by treatment group.

The subject incidence of Grade 3 and 4 nonhematological toxicities (including liver function test [LFT], CrCl) will be provided by treatment group.

10.6.3 Vital Signs

Vital sign results (systolic and diastolic blood pressure, pulse, respiratory rate, and temperature) will be summarized descriptively for baseline values, changes from baseline by visit, the minimum, maximum, and last observed values.

For the summary of changes from baseline by visit, subjects without a baseline and/or post baseline value will be excluded; values from unscheduled assessments will be

Statistical Analysis Plan: 20140355

Date: 09 Jun 2017 Page 33

excluded. Vital sign results taken > 30 days after the last administration of protocol therapy will be excluded from all vital sign summaries.

Shifts in scores for ECOG performance status scores between baseline and end of treatment visit will be tabulated by treatment group.

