Treatment regimen(s):	
Carfilzomib and dexamethasone will be administered in 28-day cycles in 1 of 2 treatment regimens. All cycles will start 28 days (\pm 2 days) after the start of the prior cycle.
 
Arm A: Once-weekly
 
• Carfilzomib 20 mg/m²
○ Study Day 1 (Cycle 1)• Carfilzomib 70 mg/m²
○ Study Days 8 and 15 (Cycle 1)• Carfilzomib 70 mg/m²
○ Study Days 1, 8, and 15 (Cycles 2+)• Dexamethasone
○ 40 mg (intravenously [IV] or orally [PO]) Study Days 1, 8, and 15 (all Cycles)○ 40 mg (IV or PO) Study Day 22 (Cycles 1 to 9 only) 
Arm B: Twice-weekly
 
• Carfilzomib 20 mg/m²
○ Study Days 1 and 2 (Cycle 1)• Carfilzomib 27 mg/m²
○ Study Days 8, 9, 15, and 16 (Cycle 1)• Carfilzomib 27 mg/m²
○ Study Days 1, 2, 8, 9, 15, and 16 (Cycles 2+)• Dexamethasone
○ 40 mg (IV or PO) Study Days 1, 8, and 15 (all Cycles)○ 40 mg (IV or PO) Study Day 22 (Cycles 1 to 9 only)
Subject selection:	Approximately 460 subjects will be randomized in this study. Subjects will be evaluated for study eligibility within the 21 days prior to randomization.

- Inclusion criteria:**
- 101.** Age \geq 18 years
 - 102.** Able to provide written informed consent in accordance with federal, local, and institutional guidelines
 - 103.** Relapsed multiple myeloma
 - 104.** Refractory multiple myeloma, defined as meeting 1 or more of the following:
 - a. Nonresponsive to most recent therapy (stable disease or PD while on treatment), or
 - b. Disease progression within 60 days of discontinuation from most recent therapy
 - 105.** At least 2 but no more than 3 prior lines of therapies for multiple myeloma
 - 106.** Prior exposure to an immunomodulatory agent (IMiD)
 - 107.** Prior exposure to a proteasome inhibitor (PI)
 - 108.** Documented response of at least partial response (PR) to at least 1 prior line of therapy
 - 109.** Measurable disease with at least 1 of the following assessed at a central laboratory within the 21 days prior to randomization:
 - a. Serum M-protein \geq 0.5 g/dL
 - b. Urine M-protein \geq 200 mg/24 hours

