10.1.2 VITAL SIGNS

Vital signs will include heart rate, blood pressure, respiratory rate, and temperature and will be assessed at Screening, prior to each administration of carfilzomib, EOT, and as needed to assess potential AEs. Clinically significant abnormal vital signs will be reported as AEs.

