13.3.3 Vital Signs

Vital sign results (systolic and diastolic blood pressure, pulse, respiratory rate, and temperature) will be summarized descriptively for baseline values and changes from baseline to the minimum, maximum, and last observed values.

For the summary of changes from baseline by visit, subjects without a baseline and/or past-baseline value will be excluded; values from unscheduled assessments will be excluded. Vital sign results taken > 30 days after the last administration of protocol therapy will be excluded from all vital sign summaries.

13.3.4 *SPARSE PHARMACOKINETIC ANALYSES*

A sparse PK sampling strategy will be employed in this study, at a subset of study sites. Blood samples will be collected at specified times, processed and stored until analysis. Concentrations of carfilzomib will be measured in plasma using a validated assay method.

The population pharmacokinetic analysis will be a cumulative analysis that will include population pharmacokinetic data obtained from previous Phase 2 and Phase 3 studies that

used intensive or sparse PK sampling. The analysis plan as well as a stand-alone pharmacokinetic analysis report will be prepared separately. The population modeling program may be used to fit a nonlinear mixed effects model to estimate PK parameters, including clearance and volume of distribution, the inter- and intra-subject variability, and the population variability in the parameter estimates. The PK concentrations obtained from subjects who participate in the sparse PK sampling, along with results from the intensive PK/PDn substudy and other carfilzomib studies, will be used in the development of a structural model. The best model will be evaluated by goodness-of-fit statistics and reduction in the objective function and posterior predictive checks. Subject characteristics such as age, gender, body weight, BSA, and race will be included in the model to identify potential covariates affecting PK of carfilzomib.

Additional analyses may be performed to evaluate the relationship between the estimated PK parameters and selected safety or clinical effect endpoints.

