13.4.4 UNSCHEDULED VISITS

Unscheduled visit measurements of laboratory data and vital signs will be included for computing worst values and/or grades.

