APPENDIX A SCHEDULE OF ASSESSMENTS (CONT'D)

Assessment	Screening ^b	Baseline ^c	All Cycles								LTFU
			D1	D2	D8	D9	D15	D16	D22	EOT	
AEs and Survival Status	—————→										
Concomitant medications	—————→										
Pregnancy Test (FCBP) ^h	X		X							X	
Survival											X

AEs = adverse events; C1D1 = Cycle 1 Day 1; C2D1 = Cycle 2 Day 1; ECHO = echocardiogram; ECG = electrocardiogram; LTFU = long-term follow-up; EOT = End of Treatment; FCBP = females of childbearing potential; MUGA = multigated acquisition; QLQ-C30 = Quality of Life Core Module; QLQ-MY20 = Quality of Life Multiple Myeloma Module; QT_c = corrected QT-interval; EQ-5D-5L = European Quality of Life-5 Dimensions.

Details of Assessments are in the protocol body.

- ^a Refer to [Section 9.1](#) for study treatment related assessment window.
- ^b Screening samples can be collected within 21 days of randomization. Refer to [Section 10.1](#).
- ^c Baseline samples are collected only after subject eligibility is confirmed. Refer to [Section 10.2](#).
- ^d Arm B only (twice-weekly regimen).
- ^e The physical examination Screening may be used if within 7 days prior to C1D1. Refer to [Section 10.1.3](#).
- ^f Full hematology and serum chemistry samples from Screening may be used for C1D1 if taken within 3 days prior to C1D1. Refer to [Section 10.4.1](#) and [Section 10.4.2](#). Beyond Cycle 4, labs will be performed on Days 1 and 15 of each cycle in both arms.
- ^g Questionnaires to be collected on Day 1 of Cycle 1, then every second cycle (Cycle 1, 3, 5, etc) during treatment and every 12 weeks (every 84 days ± 4 days) until progression, or withdrawal of consent during LTFU. Questionnaires should be completed by the subject prior to drug administration during treatment cycles. Patient convenience and satisfaction collected at Cycle 2 and EOT only. Refer to [Sections 10.7](#) and [10.10.1](#).
- ^h Urine or serum pregnancy test must be confirmed negative locally on Day 1 of each Cycle prior to dosing and at EOT. At Screening, a confirmed negative serum pregnancy test that is performed centrally is required. Refer to [Section 10.4.4](#).

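### Vital signs are scheduled 3 times per cycle in Arm A and 6 times in Arm B, so a per-subject minimum and maximum over all readings makes Arm B look more extreme with no true difference

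*SAP*

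**What the plan says.** Protocol 10.1.2 ties vital signs to dosing: they "will be assessed at Screening, prior to each administration of carfilzomib, EOT, and as needed to assess potential AEs". Arm A receives carfilzomib on three days of each 28-day cycle (1, 8, 15) and Arm B on six (1, 2, 8, 9, 15, 16). Appendix A follows this: the Day 2, 9 and 16 vital-sign entries carry footnote d, which marks them "Arm B only (twice-weekly regimen").

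For the analysis, Protocol 13.3.3.3 plans "changes from baseline to the minimum, maximum, and last observed values", and SAP 10.6.3 plans "changes from baseline by visit, the minimum, maximum, and last observed values". Both drop readings taken more than 30 days after the last dose. Both exclude unscheduled readings from the by-visit summary only. For the extremes, Protocol 13.4.4 says the opposite: "Unscheduled visit measurements of laboratory data and vital signs will be included for computing worst values and/or grades". Neither document restricts the minimum or maximum to common days, adjusts for the number of readings, or mentions the unequal schedule.

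The purpose is comparative: safety and tolerability is a secondary objective to be compared between arms (Protocol 3.2, SAP 2.2).

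**The concern.** A subject's observed maximum tends to rise, and the minimum to fall, as more readings are taken. Arm B is read twice as often per cycle, so its extremes are pushed outwards by the visit schedule alone. A reader who compares the two arms' minimum and maximum would take part of that gap for a drug effect, and the direction favours the experimental once-weekly arm.

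Timing also differs. Protocol 9.1 forbids an Arm A infusion within 5 days of the previous one, so every Arm A pre-dose reading after the first infusion comes more than 5 days after the one before it. In Arm B, three of the six readings per cycle are scheduled for the day after an infusion. The two sets of extremes are therefore drawn from different parts of the dosing week as well as from different numbers of readings.

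There is one possible route beyond the vital-sign table. Protocol 10.1.2 adds that "Clinically significant abnormal vital signs will be reported as AEs", so unequal looking could also produce some unequal adverse-event reporting.

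**Working it through.** The plan gives no figure on this point, so there is nothing to reproduce first.

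**Inputs from the documents.** Scheduled readings per cycle: 3 in Arm A and 6 in Arm B (Protocol 10.1.2, the dosing schedule, Appendix A footnote d). After c cycles that is 3c and 6c. SAP section 6 takes the Cycle 1 Day 1 value as baseline, and each arm has one end-of-treatment (EOT) reading. Dropping the former and adding the latter leaves the counts at 3c and 6c.

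**Assumptions.** No true difference between arms, equal treatment duration, and normal within-subject variation around each subject's own level. The documents give no within-subject SD, so results are in SD units.

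**Step 1: independent readings.** The expected maximum of n standard normal readings is

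E[max_n] = ∫ x · n · φ(x) · Φ(x)^(n−1) dx.

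| Cycles | Readings A / B | E[max] A | E[max] B | Gap (SD) |
|---|---|---|---|---|
| 1 | 3 / 6 | 0.846 | 1.267 | 0.421 |
| 3 | 9 / 18 | 1.485 | 1.820 | 0.335 |
| 6 | 18 / 36 | 1.820 | 2.118 | 0.298 |
| 12 | 36 / 72 | 2.118 | 2.388 | 0.270 |

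By symmetry the minimum is lower in Arm B by the same amounts. A change from baseline to the maximum shifts equally, because the baseline term is the same in both arms.

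**Step 2: correlated consecutive days.** Each Arm B next-day reading is generated as ρ·x + √(1−ρ²)·e, where x is the reading the day before and e is independent noise (100,000 simulated subjects).

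| ρ | Gap, 1 cycle (SD) | Gap, 6 cycles (SD) |
|---|---|---|
| 0 | 0.421 | 0.298 |
| 0.3 | 0.371 | 0.285 |
| 0.5 | 0.331 | 0.262 |
| 0.7 | 0.267 | 0.227 |

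**Step 3: unequal duration, illustration only.** Protocol Appendix O records superseded planning medians for PFS of 8.2 months (once-weekly) and 6 months (twice-weekly). Used as stand-ins for time on treatment, they give 3 × 8.2 × 30.4/28 = 26.7 readings in Arm A and 6 × 6 × 30.4/28 = 39.1 in Arm B, a ratio of 1.46. With 27 and 39 independent readings the gap is about 0.15 SD.

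**Step 4: scale.** For systolic pressure with an assumed within-subject SD of 10 mmHg, Steps 1 and 2 at 1 and 6 cycles span 0.227 × 10 = 2.3 to 0.421 × 10 = 4.2 mmHg. Over an assumed SD of 5 to 15 mmHg the span is 0.227 × 5 = 1.1 to 0.421 × 15 = 6.3 mmHg.

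**Step 5: what is not affected.**
- By-visit changes on Days 1, 8 and 15 compare like with like.
- The last observed value is one reading per subject however many came before, and both arms have an EOT visit.
- Safety laboratory days are the same in both arms (Protocol 10.4, Appendix A).
- ECGs are required at Screening and EOT in both arms (Protocol 10.5).

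**Step 6: after the change.** If the extremes come only from Days 1, 8 and 15 plus EOT, the count is 3 per cycle in each arm and the schedule-driven gap is 0 for equal duration.

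**The case against.** The strongest reply is that this is one descriptive table. Vital signs have no test, threshold or decision rule, and the SAP's by-visit summary already allows a like-for-like view on Days 1, 8 and 15, with Arm B's extra days shown as their own visits. The 0.42 and 0.30 SD figures also sit near the top of the plausible range: readings a day apart are likely to be correlated, and if the once-weekly regimen does delay progression, Arm A stays on treatment longer and the counts move closer together. All of this stands and limits the size and reach of the point. It does not remove it. The minimum and maximum are still planned, still unrestricted, and still serve a between-arm objective.

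Stronger readings are tempting, and the documents do not support them:

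- **That the safety comparison as a whole is tilted.** Laboratory and ECG schedules are equal, and by-visit and last values are not materially affected. The adverse-event route is possible, but nothing in the documents allows it to be sized.
- **That more Arm B subjects would be reported as crossing a blood-pressure limit.** Neither document plans a threshold incidence for vital signs.
- **That unscheduled readings should leave the worst values.** Protocol 13.4.4 requires them there, and they are not the source of the 3-versus-6 imbalance.
- **That next-day changes in Arm A would go unseen.** They are not scheduled to be measured, but Protocol 10.1.2 allows readings as needed to assess a possible adverse event. The gap is in scheduled measurement, and no analysis filter can fill it.

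**Conclusion.** The point holds in a limited form. With no true difference and equal treatment duration, the planned all-readings summary makes Arm B's expected maximum higher and its minimum lower by about 0.42 within-subject SD after 1 cycle and 0.30 SD after 6 cycles under independence, or 0.27 and 0.23 SD with a consecutive-day correlation of 0.7. Longer treatment in Arm A would shrink this further. The reading counts come from the documents. Normality, the correlation values and any translation into mmHg are assumptions.

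The effect is confined to the descriptive vital-sign minimum and maximum, and possibly to adverse events raised from them. No error rate and no efficacy conclusion depends on it. It is worth correcting because the direction favours the experimental arm in a summary that serves a secondary between-arm objective, and because the correction is almost free.

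**What to change.** In SAP 10.6.3 and Protocol 13.3.3.3:

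1. Base the between-arm minimum and maximum on the scheduled pre-dose Day 1, 8 and 15 readings plus EOT.
2. Keep the all-readings worst values, including unscheduled readings as Protocol 13.4.4 requires, in a separate table. Footnote it to say that Arm B has twice as many scheduled readings per cycle.
3. Leave the last observed values and the by-visit changes as they are.
4. State in the clinical study report that Arm A has no scheduled readings on the day after an infusion, and that the restriction to common days cannot recover them.

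The cost is a wording change, one data filter and one extra table, with no new data. The downside is that Arm B's Day 2, 9 and 16 readings leave the comparative extremes, though they remain in the all-readings table. The restriction removes the schedule effect only. If treatment duration differs, the arm treated longer will still have more readings: on the Step 3 illustration, 26.7 in Arm A against 3 × 6 × 30.4/28 = 19.5 in Arm B. The table should therefore be read alongside the duration of therapy.

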10.6.4 Electrocardiogram (ECG)

Twelve lead electrocardiograms (ECGs) including corrected QT-interval (QTc; representing the corrected duration of ventricular electrical activity) will be performed locally. Electrocardiograms will be required from all subjects at Screening and EOT. ECG results (PR, QRS, QT, QTc, heart rate, and result) will be summarized descriptively by treatment group.

10.6.5 Exposure to Investigational Product

Descriptive statistics will be produced to describe the exposure to investigational product by treatment group for subjects in the Safety Analysis Set. The number of cycles of protocol-specified therapy administered will be summarized with an additional breakdown of the number of cycles started. In addition, the duration of therapy, the cumulative dose, and the average dose per administration and relative dose intenstiy will be summarized for each drug. The number and percent of subjects with dose modifications (eg, dose reductions, dose interruptions) and reason for modification will be summarized for both treatment groups.

10.6.6 Exposure to Concomitant Medication

The number and proportion of subjects receiving concomitant medications from study day 1 through safety follow-up will be summarized by preferred term as coded by the World Health Organization Drug (WHODRUG) dictionary by treatment group in the Safety Analysis Set. In addition, the number and proportion of subjects receiving antimyeloma therapies during long term follow-up will be summarized by WHODRUG preferred term for each treatment group in the Full Analysis Set.

10.7 Pharmacokinetic or Pharmacokinetic/Pharmacodynamic Analysis Analysis plan for sparse PK data

Blood samples will be collected on Day 1 of Cycle 2 at specified times, processed and stored until analysis.

Plasma samples will be analyzed by LC–MS/MS analysis to measure the plasma concentration of carfilzomib. Sparse PK data collected from this study will be used to

Statistical Analysis Plan: 20140355

Date: 09 Jun 2017 Page 34

update a population PK model previously developed (TR-1162-171) and will be described in a separate report.

The analysis population will contain all subjects who have at least one PK sample collected according to the protocol and laboratory manual. Actual collection times will be recorded and used in the analysis. The population modeling program, NONMEM (version 7.2 or higher).will be used to fit a nonlinear mixed effects model to estimate PK parameters including clearance and volume of distribution, the inter- and intra-subject variability and the population variability in the parameter estimates. The PK concentrations obtained from subjects who participate in the sparse PK sampling along with results from the intensive PK/PDn sub-study and other carfilzomib studies will be used in the development of a structural model. The best model will be evaluated by goodness-of-fit statistics and reduction in the objective function and posterior predictive checks. Subject characteristics such as age, gender, body weight, BSA, and race will be included in the model to identify potential covariates affecting PK of carfilzomib.

Analysis plan for PK and PDn sub-study

Intensive pharmacokinetic (PK) and pharmacodynamic (PDn) samples will be obtained as a sub-study (approximately n = 15 in each arm) from subjects who consent to the additional testing at selected sites. Pharmacokinetic samples will be collected on Day 15 of Cycle 1 and PDn samples will be collected on Days 1, 5, 6, and 7 of Cycle 1 and day 2 of Cycle 2.

For both arms, PK plasma samples will be collected from all subjects for determination of plasma concentrations of carfilzomib on treatment Day 15 of Cycle 1 at the following time points:

- Predose (within 5 minutes before the start of infusion)
- 15 minutes (± 5 minutes) after the start of infusion for Arm A only (once-weekly carfilzomib)
- Immediately prior to (within 2 minutes before) the end of infusion
- 15 minutes (± 5 minutes) after the end of infusion
- 60 minutes (± 5 minutes) after the end of infusion
- 2 hours (± 5 minutes) after the end of infusion

PK

The analysis population will contain all subjects who have at least one PK sample collected according to the protocol and laboratory manual. Actual collection times will be

Statistical Analysis Plan: 20140355

Date: 09 Jun 2017 Page 35

recorded and used in the analysis. Individual and mean plasma concentration versus time data will be tabulated and plotted by dose level. The PK parameter will be estimated based on noncompartmental methods. The PK parameter estimates for carfilzomib will be summarized, including total plasma exposure (AUC, Cmax, time to maximum plasma concentration [tmax], total plasma clearance, and t1/2 [as appropriate for data collected]). Estimates for these parameters will be tabulated and summarized (i.e., n, Mean, Standard deviation, CV%, Median, Min, and Max, GeoMean and GeoCV%). These estimates will be summarized descriptively by each arm (Onceweekly vs Twice-weekly). Plasma PK parameters of carfilzomib will be computed in WinNonlin® Enterprise v.5.2 or higher.

PDn

PD analyses will be performed using a whole-blood 20S proteasome specific activity inhibition assay. The percent inhibition of 20S proteasome activity relative to baseline will be determined by a fluorogenic and/or luminescent substrate assay for the chymotrypsin-like (CT-L) (Beta5 subunit of the constitutive proteasome and LMP7 subunit of the immunoproteasome), the trypsin-like (T-L), and caspase-like (C-L) activities of the proteasome. Individual and the mean percent inhibition of 20S proteasome activity relative to baseline will be determined and will be tabulated and plotted versus nominal sampling time by each arm (Once-weekly vs Twice- weekly).

10.7.1 Exposure-Response (E-R) Analysis

PK data collected from individuals who consent to the sparse PK sampling or PK/PDn sub-study will be used to explore the E-R relationship for efficacy and safety endpoints. The data from this study will be used to update a previously developed E-R model (Amgen Pharmacometrics Report: 121604) and will be described in a separate report.

In brief, each exposure metric will be calculated using the individual subject's parameters from the population PK model (see Section 10.7 Analysis plan for sparse PK data) and dosing history. The exposure metrics will be computed from the estimated Cmax and AUC and combined with the response/adverse event data to examine the E-R relationships for efficacy and safety endpoints. A pooled analysis of data from this study and other carfilzomib clinical studies will be conducted. In addition, an E-R analysis based on this study alone may also be conducted.

Categorical responses will be tabulated by count and proportion by study. In the analysis, a quantitative assessment of the effect of each of the exposure metrics will be

Statistical Analysis Plan: 20140355

Date: 09 Jun 2017 Page 36

performed either using logistic regression for binary endpoints or log-rank test by exposure quartile for time-to-event endpoints. Endpoints exhibiting a statistically significant relationship to carfilzomib exposure will be further evaluated with multiple logistic or Cox proportional hazards models (for time-to-event endpoints) to assess the effects of covariates in conjunction with carfilzomib exposure on efficacy and safety responses. Additional multiple logistic regression analysis will not be performed on the endpoints that showed inverse relationship.

Efficacy endpoints

The efficacy endpoints will include Progression-free survival (PFS), ORR and CBR.

Safety endpoints

Safety endpoints will include the subject incidence of any grade adverse events leading to study drug discontinuation, any Grade 3 or higher adverse events, serious adverse events, TEAEs with a fatal outcome, and cardiac, hepatic, and renal adverse events. Additional endpoints of interests may be included in the analysis.

Covariates of interest

Endpoints exhibiting a statistically significant relationship to carfilzomib exposure will be further evaluated with multiple logistic models. The key covariates tested in the multiple logistic regression analysis may include the following:

bortezomib refractory in any prior regimen (yes/no), number of prior regimens, Eastern Cooperative Oncology Group (ECOG) performance status, sex, age, race, baseline CrCL, baseline hemoglobin (g/L), baseline serum beta-2 microglobulin (mg/L), and baseline platelet count (<150, ≥150 [10⁹/L]). Additional covariates of interests may be included in the analysis.

11. Changes From Protocol-specified Analyses

In the protocol, it specifies that logistic regression model will be used for ORR analysis. However, since Cochran-Mantel -Haenszel test is more widely used in analysis of binary endpoints to support regulatory filings, Cochran-Mantel-Haenszel test is specified to be used for ORR analysis in the SAP. The CMH test statistic and the score test statistic of the conditional logistic regression are approximately identical (Day N.E.& Byar D.P., 1979), so this analysis method change will not affect the conclusion of ORR analysis.

Statistical Analysis Plan: 20140355

Date: 09 Jun 2017 Page 37

12. Literature Citations / References

Clopper CJ and Pearson ES. The use of confidence or fiducial limits illustrated in the case of the binomial, Biometrika. 1934; 26(4):404-413.

Collett D. Modelling Survival Data in Medical Research. 2nd edition. London, UK: Chapman & Hall/CRC; 2003.

